9.4 Physician's Global Assessments

These assessments will be performed by the Principal Investigator, another delegated physician, or an appropriately trained medical professional (based on local requirements) who has documented training on how to perform these assessments correctly. The assessments should be made blind to the PGA-PsA and PGA-arthritis assessments.

9.4.1 Physician's Global Assessment of Psoriatic Arthritis (PhGA-PsA)

The Investigator or delegate will assess the overall status of the subject with respect to their PsA, which may include any element of the disease and may include arthritis, PSO, enthesitis, dactylitis, or spondylitis. This will be assessed using a 100mm VAS scale where 0 is "very good, asymptomatic and no limitation of normal activities" and 100 is "very poor, very severe symptoms which are intolerable and inability to carry out all normal activities". The Investigator or delegate will be asked the following question:

"Considering all the ways the disease affects your patient, mark a vertical line on the scale for how well his or her condition is today."

9.4.2 Physician's Global Assessment of Arthritis (PhGA-Arthritis)

The Physician or delegate will assess how the subject's overall arthritis appears at the time of the visit. This is an evaluation based on the subject's disease signs, functional capacity, and physical examination using a 100mm VAS scale where 0 is "very good" and 100 is "very poor". The physician will be asked to mark the Patient's arthritis:

The Patient's arthritis at this time is:

"Please mark a vertical line on the scale below to assess the overall status of the subject's arthritis signs and symptoms and the functional capacity of the subject."

Very Good-----Very Poor

9.5 Patient's Assessment of Arthritis Pain (PtAAP)

The PtAAP VAS or 'Pain VAS' is part of the ACR core set of measures in arthritis (Felson et al, 1993). Subjects will assess their arthritis pain using a VAS where 0 is "no pain" and 100 is "most severe pain."

9.6 Health Assessment Questionnaire-Disability Index score (HAQ-DI)

The HAQ-DI contains 20 items divided into 8 domains that measure: dressing and grooming, arising, eating, walking, hygiene, reach, grip, and common daily activities. Subjects are required to indicate the degree of difficulty they have experienced in each domain in the past week on a 4-point scale that ranges from 0 (without difficulty) to 3 (unable to do). Any individual score of less than 2 is adjusted to 2 if the activity requires assistance from another individual or the use of an assistive device. The highest score in each category is then summed (0 to 24) and divided by the number of categories scored to give a score that ranges from 0 to 3.

9.7 High sensitivity C-reactive protein levels (hs-CRP)

High sensitivity CRP levels will be analyzed by the central laboratory according to [Table 5-1](#).

After Screening, the hs-CRP data will not be sent to the Investigator in order to protect the blinded nature of the treatment assignments and response.

9.8 Evaluation of psoriasis

9.8.1 Body surface area psoriasis (BSA-PSO)

In the BSA-PSO assessment, the subject's hand (including the palm, fingers, and thumb) is used as the reference point for measuring how much of their skin is affected by PSO, representing roughly 1% of the body's surface.

The BSA palm method will be used for the evaluation of BSA affected by PSO as follows:

- Head and neck=10% (10 palms)
- Upper extremities=20% (20 palms)
- Trunk=30% (30 palms)
- Lower extremities=40% (40 palms)
- Total BSA=100%

9.8.2 Psoriasis Area and Severity Index (PASI)

The PASI will be assessed in all subjects with Baseline/Day 1 BSA affected by PSO $\geq 3\%$ determined by the method described in [Section 9.8.1](#) (ie, the BSA palm method).

The PASI is the most commonly used and validated assessment for grading the severity of PSO in clinical studies (Feldman, 2005). The PASI quantifies the severity and extent of the disease and weighs these with the percentage of BSA involvement.

The percent area of involvement (BSA%) is estimated across 4 body areas (head, upper limbs, trunk, and lower limbs) and then transferred into a grade ([Table 9-2](#)).

The Investigator assesses the average redness, thickness, and scaliness of lesions in each body area (each on a 5-point scale); 0=none, 1=slight, 2=moderate, 3=marked, and 4=very marked.

The PASI score ranges from 0 to 72 with a higher score indicating increased disease severity.

Table 9-2: Body areas for calculation of percent BSA for PASI

Body area	Details of area	BSA	Degree of involvement of body area ^a
Head	Face, back of head	10%	0 to 6
Upper limbs	Left, right, upper lower, flexor surface, extensor surface	20%	0 to 6
Trunk	Front, back, groin	30%	0 to 6
Lower limbs	Left, right, upper lower, flexor surface, extensor surface, including buttocks	40%	0 to 6
Total		100%	

BSA=body surface area; PASI=Psoriasis Area and Severity Index

^a Where 0=none; 1=1% to <10% affected, 2=10% to <30% affected, 3=30% to <50% affected, 4=50% to <70% affected, 5=70% to <90% affected, 6=90% to 100% affected

The PASI75, PASI90, and PASI100 responses are based on at least 75%, 90%, and 100% improvement in the PASI score. The PASI will be assessed at Screening and at Baseline/Day 1. Thereafter, the PASI will be assessed for the purposes of determining response only in subjects with PSO involving at least 3% of BSA at Baseline/Day 1.

9.8.3 Investigator's Global Assessment (IGA)

A static IGA for PSO will be used to assess disease severity in all subjects during the study. The IGA will be completed at the visits specified in [Table 5-1](#).

The Investigator will assess the overall severity of PSO using the following 5-point scale presented in [Table 9-3](#).

Table 9-3: Five-point IGA

Score	Short Descriptor	Detailed Descriptor
0	Clear	No signs of PSO; post-inflammatory hyperpigmentation may be present
1	Almost Clear	No thickening; normal to pink coloration; no to minimal focal scaling
2	Mild	Just detectable to mild thickening; pink to light red coloration; predominantly fine scaling
3	Moderate	Clearly distinguishable to moderate thickening; dull to bright red, moderate scaling
4	Severe	Severe thickening with hard edges; bright to deep dark red coloration severe/coarse scaling covering almost all or all lesions

IGA=Investigator's Global Assessment; PSO=psoriasis

The IGA responder is defined as a subject with a clear (0) or almost clear (1) assessment with at least a 2-category improvement from Baseline, meaning that this parameter will be evaluable only for subjects with psoriatic skin lesions (IGA score ≥ 2) at Baseline.

In this study, only subjects with BSA $\geq 3\%$ at Baseline will have IGA assessed at post-Baseline visits.

9.8.4 Modified Nail Psoriasis Severity Index (mNAPSI)

Subjects with psoriatic nail disease will have a target nail selected at the Baseline Visit for evaluation using the mNAPSI. The nail selected should be the most affected nail observed at Baseline and should be the only one assessed throughout the study. The target nail will be scored (0 to 3) for onycholysis/oil drop dyschromia, nail plate crumbling, and pitting and will be scored (0 for “no” or 1 for “yes”) for leukonychia, nail bed hyperkeratosis, splinter hemorrhages, and red spots in the lunula.

9.9 Minimal Disease Activity (MDA) and Very Low Disease Activity (VLDA)

Minimal Disease Activity and VLDA are states of disease activity deemed useful targets of treatment by both the subject and physician, given current treatment possibilities and limitations. Criteria covering all of the domains of the disease have been developed to determine whether or not a subject has reached MDA or VLDA based on key outcome measures in PsA (Mease, 2011; Coates et al, 2010).

A subject is considered as having MDA if 5 or more of the following 7 criteria are fulfilled:

- Tender joint count ≤ 1
- Swollen joint count ≤ 1
- PASI ≤ 1 or BSA ≤ 3
- Patient pain VAS ≤ 15
- PGA-PsA VAS ≤ 20
- HAQ-DI ≤ 0.5
- Tender enthesial points ≤ 1

A subject is considered as having VLDA if all 7 of the above criteria are fulfilled.

9.10 Disease Activity Index for Psoriatic Arthritis (DAPSA)

Disease Activity Index for Psoriatic Arthritis is a composite score of patient global and pain VAS, TJC/SJC, and hs-CRP that incorporates a pattern of peripheral arthritis that often is encountered in PsA, and is calculated as follows:

$DAPSA = SJC$ (range 0 to 66) + TJC (range 0 to 68) + PGA -Arthritis (VAS range 0 to 10cm; 0=best, 10=worst) + $PtAAP$ (VAS range 0 to 10cm) + hs -CRP

9.11 Disease Activity Score-28 based on C-reactive protein (DAS28[CRP])

The components for DAS28(CRP) include the TJC and SJC based on 28 joints (Section 9.11), CRP (Section 9.7) and the PGA-arthritis (Section 9.3.2). The DAS28(CRP) is calculated as follows:

$$DAS28(CRP) = 0.56 \sqrt{TJC} + 0.28 \sqrt{SJC} + 0.014 \text{ PGA} - \text{Arthritis} + 0.36 \ln(CRP + 1) + 0.96$$

9.12 Bath Ankylosing Spondylitis Disease Activity Index (BASDAI)

The BASDAI is the most common instrument used to measure the disease activity of AS from the subject's perspective (Garrett et al, 1994) and is considered useful for evaluating axial involvement in subjects with PsA (Fernandez-Sueiro et al, 2009). The BASDAI is a validated self-reported instrument which consists of six 10-unit horizontal numeric rating scales to measure severity of fatigue, spinal and peripheral joint pain and swelling, enthesitis, and morning stiffness (both severity and duration, respectively) over the last week (van Tubergen et al, 2015). The final BASDAI score ranges from 0 to 10, with lower scores indicating lower disease activity.

The BASDAI is calculated as follows:

$$BASDAI = \frac{Q1 + Q2 + Q3 + Q4 + \left(\frac{Q5 + Q6}{2}\right)}{5}$$

9.13 Leeds Enthesitis Index (LEI)

Enthesitis, the inflammation at the bone insertion of tendon, ligament, or joint capsule, is common in PsA. The LEI is a new enthesitis index designed for use in PsA (Healy and Helliwell, 2008) adopted for use in randomized controlled studies involving patients with PsA. Enthesitis will be assessed by palpation on the lateral epicondyles of the humerus (elbows), medial femoral epicondyles (knees), and Achilles tendons (heels) bilaterally and scored as 0=no pain and 1=painful for each of the 6 sites, for a score range of 0 to 6.

9.14 Spondyloarthritis Research Consortium of Canada (SPARCC)

The SPARCC is an index that measures the severity of enthesitis through the assessment of 16 sites (the greater trochanter [right/left [R/L)], quadriceps tendon insertion into the patella (R/L), patellar ligament insertion into the patella and tibial tuberosity (R/L), Achilles tendon insertion (R/L), plantar fascia insertion (R/L), medial and lateral epicondyles (R/L), and the supraspinatus insertion [R/L]) (Maksymowych et al, 2009). Tenderness on examination is recorded as either present (1) or absent (0) for each of the 16 sites, for an overall score range of 0 to 16.

9.15 Leeds Dactylitis Index (LDI)

Dactylitis, the swelling of an entire digit related to articular and periarticular inflammation is a characteristic of inflammatory spondyloarthropathies, including PsA. Presence of dactylitis will be assessed using the LDI basic. It measures the ratio of the circumference of the affected digit to the circumference of the digit on the contralateral hand or foot (millimeters): a minimum

difference of 10% is used to define a dactylitic digit (Healy and Helliwell, 2007; Helliwell et al, 2005). If the contralateral digit is also dactylitic, a table of normative values based on population averages is used to provide the comparison. The ratio is then multiplied by the tenderness score, using a simple grading system (0=absent, 1=present). The results from each digit with dactylitis are then summed to produce a final score. The digits involved and the matching contralateral digit will also be recorded at the same visits.

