4.3 Other variables

4.3.1 Other efficacy variables

Other efficacy variables will be assessed as specified in [Table 5-1](#) (all time points not specified in [Section 4.1.1](#) or [Section 4.2.1](#) are exploratory):

- Time to ACR20, ACR50, and ACR70 response from Baseline (Day 1)
- ACR20, ACR50, and ACR70 response

- PASI75, PASI90 and PASI100 response in the subgroup of subjects with PSO involving at least 3% BSA at Baseline
- Composite endpoint composed of ACR50 and PASI90 response in subjects with PSO involving at least 3% BSA at Baseline
- Composite endpoint composed of ACR50 and PASI100 response in subjects with PSO involving at least 3% BSA at Baseline
- Proportion of Psoriatic Arthritis Response Criteria (PsARC) responders
- Psoriatic Arthritis Disease Activity Score (PASDAS) categories
- Change from Baseline in the PASDAS
- MDA response
- Very Low Disease Activity (VLDA) response
- Proportion of subjects with an IGA score of 0 (clear) or 1 (almost clear) AND at least a 2-grade reduction from Baseline in the subset of subjects with psoriatic skin lesions at Baseline
- Disease Activity Index for Psoriatic Arthritis (DAPSA) score categories
- Change from Baseline in DAPSA score
- Change from Baseline in the Disease Activity Score-28 based on C-reactive protein (DAS28[CRP])
- Change from Baseline in all individual ACR core components:
 - SJC
 - TJC
 - HAQ-DI
 - PtAAP
 - Physician's Global Assessment of Psoriatic Arthritis (PhGA-PsA)
 - Patient's Global Assessment of Psoriatic Arthritis (PGA-PsA)
 - High sensitivity C-reactive protein (hs-CRP)
- Enthesitis-free state based on the Leeds Enthesitis Index (LEI) in the subgroup of subjects with enthesitis at Baseline
- Change from Baseline in the LEI in the subgroup of subjects with enthesitis at Baseline
- Enthesitis-free state based on the Spondyloarthritis Research Consortium of Canada (SPARCC) index in the subgroup of subjects with enthesitis at Baseline
- Change from Baseline in SPARCC index in the subgroup of subjects with enthesitis at Baseline
- Dactylitis-free state based on the Leeds Dactylitis Index (LDI) in the subgroup of subjects with dactylitis at Baseline

- Change from Baseline in the LDI in the subgroup of subjects with dactylitis at Baseline
- Proportion of subjects with a decrease of HAQ-DI from Baseline of at least 0.35 in those subjects with HAQ-DI > 0.35 at Baseline

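### Section 9.15 scores each dactylitic digit by the raw circumference ratio, so partial reduction of swelling is compressed in change from Baseline in the LDI

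*Protocol*

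**What the plan says.** Section 9.15 builds the score in four steps.

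- **Measurement.** The instrument is named ("Presence of dactylitis will be assessed using the LDI basic") and is said to measure "the ratio of the circumference of the affected digit to the circumference of the digit on the contralateral hand or foot". A table of normative values replaces the contralateral digit when that digit is also dactylitic.
- **Definition of a case.** A minimum "difference of 10% is used to define a dactylitic digit".
- **Per-digit score.** "The ratio is then multiplied by the tenderness score, using a simple grading system (0=absent, 1=present").
- **Total.** "The results from each digit with dactylitis are then summed to produce a final score".

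The protocol gives no other LDI formula. Section 4.3.1 uses the index twice among the other efficacy variables: "Change from Baseline in the LDI in the subgroup of subjects with dactylitis at Baseline" and "Dactylitis-free state based on the Leeds Dactylitis Index (LDI) in the subgroup of subjects with dactylitis at Baseline". Section 3.3 includes the effect on dactylitis among the other objectives. Table 5-1, footnote o, has circumference recorded in millimeters for all subjects at all visits after Screening.

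**The concern.** Within one paragraph, dactylitis is defined by a difference in circumference and then scored by a ratio. The two are not on the same scale. A digit at the threshold has a difference of 10% but a ratio of 1.10, so the written score adds a fixed 1 to the excess swelling of each tender dactylitic digit.

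Change from Baseline in the LDI is the continuous measure of the effect on dactylitis. Its purpose beside the binary dactylitis-free state is to register graded improvement. With the fixed 1 in place, a digit that improves substantially but stays tender and just above 10% earns little credit compared with a digit that crosses the threshold. The circumference measurements then carry less weight in the result than a reader of the endpoint would expect.

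**Working it through.** The protocol states no power or effect size for the LDI, so there is no figure to reproduce. The check is arithmetic on the formula as written.

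**Inputs, all from Section 9.15.** Ratio r = affected / comparator circumference; case definition r ≥ 1.10; tenderness t = 0 or 1; sum over dactylitic digits. Write e = r - 1 for the excess. The ratios below are examples, because the protocol gives no distribution of swelling.

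**Step 1: the constant.** As written, a tender dactylitic digit scores r = 1 + e, at least 1.10. The share of the score that is constant is 1/r:

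| r | 1/r |
|---|---|
| 1.10 | 91% |
| 1.20 | 83% |
| 1.30 | 77% |
| 1.50 | 67% |
| 1.80 | 56% |

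The share exceeds one half for any ratio below 2.0.

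**Step 2: partial improvement in a digit that stays tender and at or above 10%.** If the excess falls from e0 to e1, the written score falls by (e0 - e1)/(1 + e0), while the excess falls by (e0 - e1)/e0. The first is the second multiplied by e0/(1 + e0).

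| Ratio from, to | Fall in excess | Fall in written score |
|---|---|---|
| 1.20 to 1.10 | 0.10/0.20 = 50% | 0.10/1.20 = 8.3% |
| 1.30 to 1.15 | 0.15/0.30 = 50% | 0.15/1.30 = 11.5% |
| 1.60 to 1.30 | 0.30/0.60 = 50% | 0.30/1.60 = 18.8% |
| 1.40 to 1.12 | 0.28/0.40 = 70% | 0.28/1.40 = 20% |
| 1.50 to 1.11 | 0.39/0.50 = 78% | 0.39/1.50 = 26% |

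**Step 3: what this does to an absolute change.** Change from Baseline is a difference in points, and the constant cancels within a digit that persists: 1.40 to 1.12 gives -0.28 on either scale. It does not cancel when a digit resolves. A digit resolving from 1.40 gives -1.40 as written and -0.40 on the excess scale. The partial improvement therefore earns 0.28/1.40 = 20% of the credit for full resolution as written, against 0.28/0.40 = 70% on the excess scale. Similarly, resolution of a digit that began at 1.12 counts 1.12/0.28 = 4 times that partial improvement as written, against 0.12/0.28 = 0.43 times on the excess scale.

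**Step 4: the step at the threshold.** For a digit that began at 1.40, the drop from 1.10 to 0 is 1.10/1.40 = 79% of its Baseline score as written, against 0.10/0.40 = 25% on the excess scale. A step remains under either form, because the 10% rule creates it.

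**Step 5: what is not affected.** A digit that is not tender, or that falls below 10%, scores 0 under both forms. Resolution is captured, and a total of 0 means the same thing in both, so the dactylitis-free state is not distorted by the constant.

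**The case against.** The strongest reply is that Section 9.15 is a short account of a named, cited instrument, and that scoring detail belongs to the SAP. Section 14 refers to the SAP for more detail on methods, and Section 14.3.2 does so for the other efficacy variables. The SAP may already give the formula in another form, and the word ratio may be loose shorthand for the percentage difference in the preceding sentence. This lowers the severity but does not remove the point. Section 9.15 states a complete rule and does not defer it, whereas Section 9.1.1 expressly sends its data mapping to the SAP. If the SAP subtracts 1, the two documents disagree; if it follows the protocol, the arithmetic above applies.

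Whether the wording departs from the published index cannot be judged from the protocol, and nothing here relies on the cited papers. That is a reason to check the correction against them. It is also fair to say that ranking several mildly swollen digits above one severely swollen digit is a choice between extent and severity, not an error in itself.

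Three stronger readings are tempting and are not supported:

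- **That a digit scores 1 with no swelling.** Only dactylitic digits are summed, so a digit without qualifying swelling scores 0.
- **That the endpoint loses most of its ability to show improvement.** Only partial improvement in a digit that stays tender and above threshold is compressed, and no loss of power has been shown.
- **That the change score is in effect a digit count.** How close it comes depends on swelling ranges that the protocol does not give. An illustrative simulation assumed 1 to 5 tender digits at Baseline, excess uniform from 10% up to 30%, 50% or 80%, 0 to 120% of the swelling remaining, and 60% of digits still tender. R-squared between change in score and change in the count of tender dactylitic digits was 0.995, 0.98 and 0.95 as written, and 0.84, 0.70 and 0.61 on the excess scale. None of these assumptions comes from the protocol, so the result shows only the direction. Even the excess form follows the count to a considerable degree.

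**Conclusion.** The point holds, at minor severity. As written, each tender dactylitic digit carries a fixed 1, which is 91% of its score at the threshold and 67% at a ratio of 1.50. Partial reduction of swelling is understated relative to resolution, as in the example of 20% against 70%. The formula and the direction follow from Section 9.15 alone; the size for any given subject depends on the ratios that occur.

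The consequences are limited. Change in the LDI is one of the other efficacy variables, is outside the fixed testing sequence, is summarized descriptively under Section 14.3.2, and concerns only subjects with dactylitis at Baseline. The PASDAS in Section 9.23 uses a separate count of tender dactylitic digits. Because circumferences are recorded in millimeters, the score can be recomputed and no information is lost. The conclusion assumes that Section 9.15 would be programmed literally.

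**What to change.** In Section 9.15, state the per-digit term as percent excess circumference, (ratio - 1) x 100, multiplied by tenderness (0 or 1), and sum it over digits that meet the existing 10% definition. A tender digit at the threshold then scores 10, and halving the excess of a digit that remains tender and dactylitic halves its contribution.

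Before unblinding, confirm that this matches the cited LDI basic scoring and the SAP, so that all three give one formula. If the raw ratio is intended, say so in Section 9.15 and note its limited sensitivity to partial improvement.

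The cost is one formula line and the matching derivation in the analysis programs. No new data, visits or procedures are needed, and the 10% definition stays as it is.

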9.16 Psoriatic Arthritis Quality of Life (PsAQoL)

The use of the PsAQoL is recommended by the health regulatory authorities as 1 of the disease-specific HRQoL measures in PsA (CHMP/EWP/438/04). The PsAQoL comprises 20 items so that the score ranges from 0 to 20 with higher scores indicating worse HRQoL.

9.17 Psoriatic Arthritis Impact of Disease-12 (PsAID-12)

The PsAID-12 is a patient-reported outcome measure for assessing the impact of PsA in 12 physical and psychological domains, including pain, fatigue, skin problems, work and/or leisure activities, functional capacity, discomfort, sleep disturbance, coping, anxiety/fear/uncertainty, embarrassment and/or shame, social participation, and depression. Each domain is assessed with a single question using a 0 to 10 numerical rating scale. Each domain score is multiplied by a weighting factor and the results are then summed to provide the total score. The total score ranges from 0 to 10, with higher scores indicating a worse status. The PsAID-12 demonstrated satisfactory psychometric properties in an international validation study; however, further validation is needed (Gossec et al, 2014). A score below 4 out of 10 is considered a patient-acceptable status. A change of 3 or more points is considered relevant absolute change.

